## 7.2 Future Use of Lab Specimen

Serum specimens remaining after completion of all immunogenicity analysis for the trial are planned to be stored for future analysis supporting the licensure path of MVA-BN®. Future analyses would facilitate bridging trial data to animal immunogenicity data and/or to immune response data collected from subjects vaccinated with conventional smallpox vaccines.

Subjects will be asked for consenting to future storage / use of samples and will be informed about data protection measures. Specimens will be stored in BN’s secured laboratory area or at an external storage facility in a coded, anonymized manner to ensure data protection. Genetic testing will not be performed.

### **7.3 Measurement of the Take**

A digital photograph will be taken of the vaccination site at the visits 6-8 days and 13-15 days after scarification with ACAM2000®.

The system for capturing the digital photographs and measuring the area of the lesion is described in detail in the ITRC Charter.

The ITRC will confirm the correct measurement of the lesion area by reviewing blinded subject profiles (as described in the ITRC Charter). Statistical calculations for attenuation of take will be based on the ITRC confirmed lesion areas.

The healing will be confirmed by the investigator at the appropriate scheduled visit.

### **7.4 Assessment of ACAM2000® Vaccination Site**

The vaccination site will be examined by the Investigator or designee on Day 0 (prior to vaccination), and Days 7, 14 and 28 post vaccination with ACAM2000®. The day 6-8 examination (Visit 8 for Group 1 and Visit 2 for Group 2) is critical to the determination of a successful vaccination, and the day 13-15 examination (Visit 9 for Group 1 and Visit 3 for Group 2) is critical to the determination of the co-primary endpoint and subjects should be strongly encouraged to return for these clinical visits on schedule. The examiner shall wear protective gloves during each examination.

During the examination, the vaccination site will be examined and scored for the following parameters:

- healing time (i.e. number of days until scab separates from the skin)
- major lesion diameter (mm)
- major erythema diameter (mm)
- major induration diameter (mm).

If the shape of the lesion, erythema and induration observed is not round but rather asymmetrical then the maximum cross-sectional measurement would be recorded.

The type of lesion will also be noted (specifying papule, vesicle, pustule, ulcer, crust or scab).

In the unlikely circumstance that there is more than one lesion, this fact will be noted in the CRF but the satellite lesions would not be measured.

Individual take rates will be classified as either full, partial or absent take. The categorization will be in line with the World Health Organization (WHO) criteria for a “Major Reaction” as listed in

the US Health Affairs [Memorandum issued by the US Assistant Secretary of Defense in April 2008](#) ([Appendix IVf](#); [Section 17.10](#)), namely:

A vesicular (blistery) or pustular (pus-filled) lesion or area of definite palpable induration or congestion surrounding a central lesion that might be a crust or an ulcer.

After primary (first) vaccination, the vaccination site usually progresses as follows (and will be referred to as “full take” in the POX-MVA-006 CTP):

- The inoculation site becomes reddened and pruritic 3 to 4 days after vaccination.
- A vesicle surrounded by a red areola then forms, which becomes umbilicated (collapsed center) and then pustular by days 7 to 11 after vaccination.
- The pustule begins to dry; the redness subsides; and the lesion becomes crusted between the second and third week, the scab falls off, leaving a permanent scar that at first is pink in color but eventually becomes flesh colored.

## 7.5 Independent Take Review Committee

BN has established the blinded ITRC consisting of 3 physicians experienced in scarification of replicating smallpox vaccines. The ITRC will assess the responses of subjects vaccinated with ACAM2000®. This committee will act independent of the DSMB. The purpose of having an ITRC to review subject profiles is to provide an independent determination of take responses and to assure a consistent evaluation of subject responses. A Charter describes the details of the committee’s requirements, organization and obligations.

The ITRC’s determinations will be considered the source data for the analysis of the individual takes observed in the MVA-BN®-experienced ACAM2000® boosted subjects (Group 1) and the MVA-BN®-naïve ACAM2000® vaccinated subjects (Group 2).

More information on the ITRC’s assessment criteria can be found in the ITRC Charter.

## 8 Safety and Reactogenicity

Taking into account the medical history of the subject, safety will be monitored by performing physical examinations including vital signs, routine laboratory measurements as well as by evaluating local and general solicited AEs and unsolicited AEs.

Using replication-competent 1st and 2nd generation vaccinia-based smallpox vaccines during smallpox vaccination programs in the USA during the last years, cases of acute myocarditis and pericarditis were observed ([Cassimatis, 2004](#)). Therefore special cardiac monitoring assessments will be performed.

## **8.1 Definitions**

### **8.1.1 Medical History**

Symptoms present before or at the screening visit will be documented in the medical history.

### **8.1.2 Baseline Signs and Symptoms**

Any new signs, symptoms or changes in health starting after ICD signed and before the first vaccination will be recorded in the "baseline signs and symptoms" section of the CRF and in the subject's research record. Symptoms starting prior to ICD being signed will be documented in medical history.

### **8.1.3 Adverse Events**

New signs, symptoms or changes in health starting after the first vaccination are documented in the AE section. AEs are recorded based on unsolicited and solicited questioning ([Section 8.1.3.1](#) and [8.1.3.2](#)).

#### **8.1.3.1 Unsolicited Adverse Events**

Unsolicited AEs are defined as any untoward (undesirable) occurrence of a medical event in a clinical trial subject temporally associated with the administration of an Investigational Medicinal Product (IMP) or a medical product (MP) which does not necessarily have a causal relationship with this IMP/MP. Up to Visit 10 all AEs (e.g. feeling of ill-health, subjective symptoms and objective signs, intercurrent diseases, accidents, etc.) observed by the investigator and/or reported by the subject must be recorded in the CRF regardless of the assessment of causality in relationship with the IMP/MP.

Abnormal laboratory values assessed as being clinically significant by the investigator are to be documented as AEs. In addition, abnormal laboratory values fulfilling the Grade 3 or Grade 4 criterion according to the toxicity scale ([Appendix I; Section 17.1](#)) are to be documented as AE in the CRF, regardless of whether they are considered clinically relevant or not. Toxicity grade and seriousness of an AE will be assessed separately, i.e. a Grade 3 or Grade 4 AE will not automatically be regarded as serious.

At every trial visit up to Visit 10 in Group 1 and up to Visit 4 in Group 2, the investigator will ask the subject if they have experienced any AEs since their last visit. All intercurrent diseases reported by the subject need to be recorded by the investigator in the appropriate page of the CRF.

#### **8.1.3.2 Solicited Adverse Events**

Within this CTP solicited AEs are defined as all symptoms specifically listed in the memory aid provided to the subjects following each vaccination. The subjects are requested to monitor and record local symptoms (i.e. pain, redness (erythema), swelling, induration, itching (pruritus) and

vaccination site appearance (normal/healed, red spot, bump, reddish blister, whitish blister, scab, ulcer/crater, warmth, swollen >3in, red streaks, drainage) as well as general symptoms (i.e. body temperature, headache, muscle pain (myalgia), chills, nausea, fatigue, malaise, swollen lymphnodes) in the memory aid daily for the day of vaccination and the following 14 days (days 0-14, 15 day period). Any symptoms persisting beyond Day 14 post vaccination are recorded in a memory aid extension. The definition of AEs originates from the MVA-BN® Investigator's Brochure and the ACAM2000® Prescribing Information ([Appendix IVc](#); [Section 17.7](#)).

### 8.1.3.3 Adverse Event of Special Interest

An AESI is defined in this trial as:

- Any cardiac sign or symptom developed since the first vaccination
- ECG abnormalities determined to be clinically significant
- Cardiac enzyme troponin I  $\geq 2 \times$  ULN ( $\geq$ Grade 2; see toxicity scale, [Appendix I; Section 17.1](#))

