## 8.2.7 Cardiac Assessment

To evaluate the cardiac profile of MVA-BN®, targeted physical exams including auscultation of the heart and lung will be performed ([Section 8.2.3](#)). Any kind of cardiac signs (i.e. discovered by the physician during examination of the subject) or symptom(s) (i.e. experienced and reported by the subject) detected during the trial such as but not limited to chest pain, dyspnea, arrhythmia or edema are recorded.

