### Questions:

The following specific cardiac questions will be routinely asked to the subject at the trial visits on the day of each vaccination; and the trial visits 2 weeks following each vaccination (Visits 3, 6

and 9 for Group 1; Visit 3 for Group 2) and 4 weeks following each vaccination (Visits 4, 7 and 10 for Group 1; Visit 4 for Group 2).

- Since your last visit, have you developed any chest pain, pressure, or discomfort that is beyond what is usual for you?
- Since your last visit, have you developed any shortness of breath at rest or exertion that is beyond what is usual for you?
- Since your last visit, have you noticed any swelling of your ankles, feet, or legs that is beyond what is usual for you?

If the answer to one of the question is "yes", further evaluations as outlined in [Figure 1](#) are initiated.

[figure not shown]
Subjects who develop any kind of cardiac signs or symptoms during the trial such as, but not limited to chest pain, dyspnea, arrhythmia or edema are referred to a local cardiologist for cardiac evaluation as described in the DoD Clinical Guidelines for Post-Smallpox Vaccine Associated Myopericarditis ([Appendix II; Section 17.2](#)). All treatment emergent AESIs will be followed up until complete resolution or until the sequelae are stable and considered to be permanent.

In any case of cardiac signs or symptoms, or increased laboratory results for Troponin I, the subject will be asked to attend for an unscheduled visit at the site, in order to perform or repeat Troponin I testing, to perform a physical examination for cardiac symptoms and to record an unscheduled ECG.

Further details regarding the follow-up of AESIs are described in the 'Investigator's Manual – Follow-up of Adverse Events of Special Interest'.

[Figure 1](#) outlines the algorithm for assessment of cardiac events.

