### **Safety and Reactogenicity**

Occurrence, relationship to vaccine and intensity of any SAE.

Occurrence of any cardiac sign or symptom indicating a case of myo-/pericarditis, i.e. AESIs

Occurrence of any Grade 3 or 4 AEs possibly, probably or definitely related to vaccine within 28 days after each vaccination.

Occurrence, relationship to vaccine and intensity of any non-serious AEs within 28 days after each vaccination.

Occurrence of solicited general AEs (body temperature, headache, myalgia, chills, nausea, fatigue, malaise, swollen lymph nodes) within 15 days after each vaccination (days 0-14): Intensity, duration and relationship to vaccination.

Occurrence of solicited local AEs (pain, redness (erythema), swelling, induration, itching (pruritus), and vaccination site appearance (normal/healed, red spot, bump, reddish blister, whitish blister, scab, ulcer/crater, warmth, swollen >3in, red streaks, drainage) within 15 days after each vaccination (days 0-14): Intensity and duration.

Daily measurement of lesion size, erythema and induration based on physical appearance of vaccination site as documented in the memory aid.

- major lesion diameter (mm) each day
- major erythema diameter (mm) each day
- major induration diameter (mm) each day

If the shape of the lesion, erythema (excludes lymphangitis) and induration observed is not round but rather asymmetrical then the largest (or major) cross-sectional measurement would be recorded.

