### 5.1.3 Myocarditis and Pericarditis in the ACAM2000 Clinical Trial Experience

In clinical trials involving 2983 subjects who received ACAM2000 and 868 subjects who received Dryvax®, ten (10) cases of suspected myocarditis [0.2% (7 of 2983) ACAM2000 subjects and 0.3% (3 of 868) Dryvax® subjects] were identified. The mean time to onset of suspected myocarditis and/or pericarditis from vaccination was 11 days, with a range of 9 to 20 days. All subjects who experienced these cardiac events were naïve to vaccinia. Of the 10 subjects, 2 were hospitalized. None of the remaining 8 cases required hospitalization or treatment with medication. Of the 10 cases, 8 were sub-clinical and were detected only by ECG abnormalities with or without associated elevations of cardiac troponin I. All cases resolved by 9 months, with the exception of one female subject in the Dryvax® group, who had persistent borderline abnormal left ventricular ejection fraction on echocardiogram. The best estimate of risk for myocarditis and pericarditis is derived from the Phase 3 ACAM2000 clinical trials where there was active monitoring for potential of myocarditis and pericarditis. Among vaccinees naïve to vaccinia, 8 cases of suspected myocarditis and pericarditis were identified across both treatment groups, for a total incidence rate of 6.9 per 1000 vaccinees (8 of 1,162). The rate for the ACAM2000 treatment group were similar: 5.7 (95% CI: 1.9-13.3) per 1000 vaccinees (5 of 873 vaccinees) and for the Dryvax® group 10.4 (95% CI: 2.1-30.0) per 1000 vaccinees (3 of 289 vaccinees). No cases of myocarditis and/or pericarditis were identified in 1819 previously vaccinated subjects. The long-term outcome of myocarditis and pericarditis following ACAM2000 vaccination is currently unknown.

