15.3.2 Serious Adverse Events and Adverse Events of Special Interest

- 15.3.2.1 Serious Adverse Events: Incidence by Preferred Term and System Organ Class – FAS
- 15.3.2.2 Adverse Events of Special Interest: Incidence by Preferred Term and System Organ Class – FAS
- 15.3.2.3 Adverse Events of Special Interest (Per Vaccination Period): Cardiac Follow-Up – FAS

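### The myo-/pericarditis safety endpoint is equated with a broad AESI count: no planned output gives subjects by case level, and serious AESIs are removed from the count

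*Protocol*

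**What the plan says.** Protocol 9.3.2 lists the endpoint as "Occurrence of any cardiac sign or symptom indicating a case of myo-/pericarditis, i.e. AESIs". The synopsis and SAP 1.4.4 say the same in substance.

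Protocol 8.1.3.3 defines an AESI by any one of three criteria:
- "Any cardiac sign or symptom developed since the first vaccination"
- "ECG abnormalities determined to be clinically significant"
- "Cardiac enzyme troponin I" at or above 2 x ULN

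Protocol 8.2.7 reads the first criterion widely: signs or symptoms "such as but not limited to chest pain, dyspnea, arrhythmia or edema are recorded". Subjects are asked scripted questions, for example "have you developed any shortness of breath at rest or exertion that is beyond what is usual for you", and a yes starts further evaluation.

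Protocol 8.2.7 gives investigators the Appendix III definitions so that they can recognise possible cases and separate them from non-specific ECG findings. It asks for a judgement of clinical significance and requires cardiology referral, troponin testing, examination and an unscheduled ECG.

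SAP 3.10.9 compares subjects with at least one SAE between groups by Fisher's exact test and reports AESIs in the same way. Table 15.3.2.2 is titled "Adverse Events of Special Interest: Incidence by Preferred Term and System Organ Class". Table 15.3.2.3 and Listing 16.2.3.2.5 cover cardiac follow-up of AESIs, without stated content. The SAP's General Definitions and 3.9.2 send any AESI that is also serious to the SAE analysis; the General Definitions exclude it from the AESI analysis.

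**The concern.** The endpoint's name promises cases of myo-/pericarditis, but the planned count is of anyone who meets one broad criterion. In the pooled count, breathlessness beyond the usual with normal ECG and troponin weighs the same as symptoms with ECG change and raised troponin.

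The preferred-term table separates these only if someone enters myocarditis or pericarditis as the diagnosis. Its rows cannot show which subjects had symptoms together with an objective finding.

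The serious-AESI rule then works in the opposite direction from what a case count needs: a hospitalised case leaves the AESI count and isolated ankle swelling stays. No named output brings the two together as cases.

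What is at stake is interpretation. Myo-/pericarditis is the special-interest risk of the comparator, and a reader of the report would not be able to take a case count from the AESI total.

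**Working it through.** **1. The benchmark case rate.** The ACAM2000 label (Protocol Appendix IVc, label section 5.1.3) gives "5.7 (95% CI: 1.9-13.3) per 1000 vaccinees (5 of 873 vaccinees" for vaccinia-naive recipients. 5/873 = 5.73 per 1000, with an exact Clopper-Pearson interval of 1.86 to 13.31 per 1000, so the figure reproduces. (Protocol 2.3 prints 5.73 beside seven subjects; the fraction that gives 5.73 is 5/873.)

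**2. A proxy for non-specific symptoms.** Label Table 3 gives dyspnea in 39 of 873 vaccinia-naive ACAM2000 recipients: 39/873 = 4.47%.

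**3. Expected counts in one group of 220 (Protocol synopsis).**
- Suspected cases: 220 x 5/873 = 1.26. Over the label's interval: 220 x 0.0019 = 0.4 to 220 x 0.0133 = 2.9.
- Chance of at least one suspected case: 1 - (1 - 5/873)^220 = 72%.
- Dyspnea reports: 220 x 39/873 = 9.8.
- Ratio: 39/5 = 7.8 to 1.

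**4. Does the broad definition cost a detectable difference?** I summed the binomial probabilities of all outcomes with two-sided Fisher p <= 0.05, with 220 per group and all true cases in one group.

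| Definition | Rates compared | Power |
|---|---|---|
| Cases only | 0.57% vs 0% | 0.2% |
| Cases only, upper CI limit | 1.33% vs 0% | 7.5% |
| Broad, 4.47% background | 5.04% vs 4.47% | 3.6% |
| Broad, 4.47% background, upper CI limit | 5.80% vs 4.47% | 6.4% |
| Broad, assumed 2% background | 2.57% vs 2% | 3.1% |
| Broad, assumed 10% background | 10.57% vs 10% | 3.9% |

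Power is negligible in every row.

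**5. Where a case would appear.** Set side by side, the planned outputs treat three kinds of subject as follows:
- Symptom only, work-up normal: if it remains an AESI, it is in the AESI count under the symptom term.
- No symptom, ECG or troponin change only: in the AESI count, possibly under an investigation term. The label says 8 of its 10 suspected cases were of this sub-clinical kind. Appendix III requires symptoms even for a possible case, so its levels alone would miss them.
- Symptoms with objective findings and hospitalised: in the SAE analysis, absent from the AESI count.

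**6. Vaccination periods.** After vaccination, the cardiac questions are asked at six visits in Group 1 (Visits 3, 4, 6, 7, 9, 10) and two in Group 2 (Visits 3, 4). A count per subject over the whole trial gives Group 1 more opportunity for a non-specific yes, so any case table needs to be by period.

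**The case against.** The strongest reply is that case criteria are present. Investigators hold the CDC definitions, judge clinical significance, and refer subjects with cardiac signs or symptoms to a cardiologist. That stands: what is missing is the use of those criteria in the endpoint and tables.

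Second, the outputs are richer than one table. Cardiac follow-up is tabulated per vaccination period and listed by subject, troponin abnormalities and ECG shifts have their own tables, and Protocol 9.6 has each SAE described individually. Equal weighting therefore applies to the pooled count, not to everything reported. The content of the follow-up table is not given, so it may show part of what is needed. The figures with the cardiac and AESI-reporting algorithms are not reproduced, and the Investigator's Manual is a separate document, so how a yes is finally coded after a normal work-up cannot be seen.

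Third, the dyspnea rate is weak evidence. It comes from a diary checklist in another trial; here dyspnea is not in the memory aid but is asked about at visits, relative to what is usual for the subject. The 7.8 to 1 ratio is a proxy and nothing more.

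Fourth, the label (section 5.1) describes its 5.7 per 1000 in terms of chest pain, raised enzymes or ECG abnormalities, which overlap the AESI criteria. It would be too strong to say that no comparison with it is possible. The difficulty is that the pooled count does not show which AESIs are comparable.

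**Conclusion.** The point holds as one of endpoint definition and reporting. The planned AESI count does not measure the endpoint it is named for, no planned variable or named table gives subjects by case level, and serious cases are taken out of the count. If the label rates carried over, a group of 220 ACAM2000 recipients would have about 10 dyspnea reports beside about 1.3 suspected cases (0.4 to 2.9).

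A reader might infer that the broad definition swamps a safety signal or pulls the ratio between groups towards 1. The documents do not support that. They give no AESI background rate for this trial's way of asking, serious cases leave the AESI count in any event, and a comparison of cases alone would have 0.2% to 7.5% power. Secondary comparisons are declared descriptive (Protocol 9.6). With about one case expected, the value lies in classifying it correctly and showing it.

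**What to change.** Keep the AESI definition in Protocol 8.1.3.3 unchanged as the trigger for work-up. In SAP 3.10.9 and Section 15.3.2, add one table by group and vaccination period that includes serious AESIs, notwithstanding the exclusion in the General Definitions, and counts subjects:

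1. by qualifying criterion: symptom only; ECG and/or troponin only; symptom plus ECG and/or troponin;
2. by investigator-assigned Appendix III level: not a case, possible, probable, confirmed.

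Both parts are needed, because Appendix III classifies symptomatic cases and the label's cases were mostly sub-clinical. A footnote should say that ECG and troponin are scheduled after the first and third Group 1 vaccinations but only if clinically indicated after the second, so findings without symptoms are less likely to be detected in that period.

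The cost is one added field on the AESI eCRF page for the Appendix III level (none if it is already captured), SAP wording and one table. The ECG, troponin and cardiology data come from work-up already required. The downside is that the case counts will be small and can only be read descriptively.

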### 8.1.3.4 Serious Adverse Events

A SAE is any untoward medical occurrence or reaction that at any dose:

- Results in death
- Is life-threatening  
The term "life-threatening" in the definition of "serious" refers to an event in which the subject was at risk of death at the time of the event; it does not refer to an event which hypothetically might have caused death, if it were more severe.
- Requires in-patient hospitalization or prolongation of existing hospitalization
- Results in persistent or significant disability or incapacity
- Is a congenital anomaly or birth defect
- or is an otherwise important medical event, e.g.
  - leads to suspicion of transmission of an infectious agent
  - suggests lack of efficacy of the product
  - documents an overdose of the product

Medical and scientific judgment should be exercised in deciding whether expedited reporting is appropriate in other situations, such as important medical events that may not be immediately life-threatening or result in death or hospitalization but may jeopardize the subject or may require intervention to prevent one of the other outcomes listed in the definition above. These should also usually be considered serious.

Examples of such events are intensive treatment in an emergency room or at home for allergic bronchospasm; blood dyscrasias or convulsions that do not result in hospitalization; or development of drug dependency or drug abuse.

